OCTOM	Office of Clinical Trials Operations and Management, NIDCR, NIH
OHRP	Office for Human Research Protections
OHRQoL	Oral Health-Related Quality of Life
OHSR	Office of Human Subjects Research
PBRN	National Dental Practice Based Research Network
PD	Protocol Deviation
PI	Principal Investigator
PO	Program Official, NIDCR, NIH
PS	Project Scientist, NIDCR, NIH

QA	Quality Assurance
QC	Quality Control
SAE	Serious Adverse Event/Serious Adverse Experience
SOP	Standard Operating Procedure
UP	Unanticipated Problem
US	United States

PROTOCOL SUMMARY

Title: Dental Implant Registry

Précis: Dental rehabilitation of partially and fully edentulous patients with endosseous implants has become a routine treatment modality, and it is estimated that up to 5 million dental implants are placed each year. There is a body of literature to suggest that biological and prosthetic complications occur, which may interfere with the health of the peri-implant tissues and the function and esthetics of the implant restoration. The purpose of this prospective, observational study conducted within the National Dental Practice-Based Research Network (PBRN) is to quantify the incidence of biologic and prosthetic complications and assess risk factors for implant complications.

Approximately 200 practitioners from 6 Regional Network Nodes will be recruited to enroll approximately 1550 patients with approximately 2000 implants for longitudinal observation. Patients will be enrolled at the time of implant prosthetic placement. Baseline patient demographic and characteristics, mucosal and prosthetic characteristic data and radiographic images taken for standard of care purposes will be obtained. Follow-up clinical data and standard of care radiographic images will be collected at 1, 2, and 3 years after prosthetic placement.

Objectives and Outcomes:

Primary objective: quantify the incidence of biologic and prosthetic complications amongst patients receiving dental implant therapy in a practice setting.

Primary outcomes: biologic (peri-implant mucositis, peri-implantitis, implant failure), and prosthetic complications that have compromised implant esthetics and/or function.

Secondary objectives:

- Determine risk factors for biologic and prosthetic complications amongst patients receiving dental implant therapy in a practice setting.
- Assess patient OHRQoL (Oral Health-Related Quality of Life) and satisfaction with esthetics and function following implant therapy.

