Secondary outcomes: Patient, surgical, prosthetic risk factors; biologic and prosthetic complications, and OHRQoL.

[figure not shown]
Tertiary objectives:

- Explore the influence of prosthesis type on the incidence of prosthetic and biologic complications in a private practice setting.
- Explore factors predictive of patient OHRQoL (which includes satisfaction with esthetics and function).

Tertiary outcomes: Surgical and prosthetic factors; biologic and prosthetic complications, OHRQoL.

Population:	Approximately 200 National Dental PBRN practitioners from all six regional nodes will enroll approximately 1550 patients planned to undergo implant prosthetic placement to contribute approximately 2000 dental implants for longitudinal observation.
Study Duration:	Approximately 5 years
Subject Participation Duration:	Approximately 3 years for patients and approximately 4 years for practitioners
Estimated Time to Complete Enrollment:	Practitioner Enrollment = approximately 12 months Patient Enrollment = approximately 12 months

Schematic of Study Design:

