
Assess patient Oral Health-Related Quality of Life (OHRQoL) and satisfaction with esthetics and function following implant therapy.
	
Patient centered outcomes are an important aspect of the overall outcomes of treatment. The patients' satisfaction with the esthetics, health and function will be collected by patient surveys. Changes in the overall OHRQoL and patient satisfaction will be reported.
	
Patients will complete OHRQoL surveys at baseline and follow-up visits. For patient satisfaction, surveys will be administered describing esthetics, function and health prior to the insertion of the implant prosthesis (baseline) and after insertion (follow-up).
	
The patient survey instruments are completed by the patients prior to insertion of the prosthesis, and at the 1-3-year follow-up visits.

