3.3 Tertiary/Exploratory

Objective	Brief Description/Justification of Outcome Measure	Outcome Measured By	Time Frame
Explore the influence of prosthesis type on the incidence of prosthetic and biologic complications in a private practice setting.	The influence of the prosthesis on both prosthetic and biologic complications has been described in the literature. This analysis will explore therapies and strategies associated with dental implant success and that minimize prosthetic or biologic complications.	The incidence of biologic and prosthetic complications will be determined for each type of prosthesis (described above).	Data are collected at baseline and at the 1-3-year annual follow-up visits.
Explore factors predictive of patient OHRQoL (which includes satisfaction with esthetics and function).	The data will be used to construct models to explore the predictive factors for patient success. Data for model inclusion will include baseline patient specific data, surgical data, and prosthetic follow-up data. Peri-implant health and prosthetic performance will also be included.	The OHRQoL will be used to examine the association between patient/implant/therapy factors and the OHRQoL score.	Data are collected at baseline and at the 1-3-year annual follow-up visits.

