- Clinical examination of the prosthesis: Screw fracture, Screw loosening, Loss of screw, Structural fracture, Resin fracture, Porcelain fracture, Loss of retention, Loss of filling covering screw, Abutment/implant misfit, Abutment/prosthesis misfit, Cement remnants present, Wear of the occlusal surfaces.
- Radiographs: Practitioners will submit digital radiographs of each study implant, taken at baseline (after implant prosthetic placement) and at annual follow-up visits 1, 2, and 3 years following prosthetic placement. The radiograph should be void of any identifiers. Radiographs will be uploaded to the centralized study database provided by the NCC. Node Coordinators will review the radiographs and remove identifiers if present. The study team completes the final review to determine whether the radiograph is sufficient quality to be included in the radiograph repository. If the radiograph is insufficient quality, the study team will work with the Node Coordinator to provide feedback, if applicable, and determine whether a higher quality radiograph can be found. Radiographs in the radiograph repository will go through the adjudication process, where trained and calibrated evaluators assess the radiograph for quality and will determine peri-implant bone height measurements and prosthetic fit for each implant.

Patients

Patient questionnaires will ascertain patient satisfaction and OHRQoL thought to be important patient-reported outcomes. Patient satisfaction with function and esthetics will be measured with the OHRQoL.

Baseline: At the implant prosthetic placement visit, patients will complete the *Baseline Patient Demographics, Patient Contact Survey, Patient Characteristics Survey and Baseline Oral Health Quality of Life (ORHQoL) Survey*, which will ascertain information related to: 1) demographics, 2) socioeconomic variables, 3) medication use, 4) medical conditions, 5) satisfaction with function and esthetics prior to implant therapy, and 6) oral health quality of life prior to prosthetic implant therapy.

Annual follow-up: Patients will complete the *1-, 2-, or 3-Year Patient Annual Follow-Up Survey, which includes the OHRQoL survey and Patient Contact survey*, to ascertain patient information related to: 1) Contact information changes 2) Changes in health history, medications and smoking habits, 2) OHRQoL following prosthetic implant therapy.

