Bone Grafting at time of implant placement	biologic complications
Immediate loading	biologic complications
Reason for tooth loss: Periodontitis	biologic complications
Reason for tooth loss: Endodontic failure	biologic complications
Reason for tooth loss: Caries	biologic complications
Reason for tooth loss: Trauma	biologic complications
Congenitally missing	biologic complications
Removable prosthesis	biologic complications
Poor prosthetic fit	biologic complications
Emergence angle	biologic complications
Cement remnants present	biologic complications
Open contacts present	biologic complications
Single tooth restoration	biologic and prosthetic complications
Multiple unit restoration splinted	biologic and prosthetic complications

Cemented restoration	biologic and prosthetic complications
Custom abutment	biologic and prosthetic complications
Stock abutment	biologic and prosthetic complications
Removable prosthesis full arch	prosthetic complications
Removable prosthesis: poor retention	prosthetic complications
Screw retained prosthesis	prosthetic complications
Opposing dentition: Natural	prosthetic complications
Opposing dentition: Complete denture	prosthetic complications
Opposing dentition: Partial denture	prosthetic complications
Occlusion: Mutually protected	prosthetic complications
Occlusion: Group function	prosthetic complications
Prosthesis material: Porcelain	prosthetic complications
Prosthesis material: Zirconia	prosthetic complications
Prosthesis material: Plastic	prosthetic complications
Prosthesis material: Zirconia with Porcelain veneer	prosthetic complications

Tertiary (exploratory) Objectives. To explore the OHRQoL (Oral Health-Related Quality of Life) following implant therapy, and to explore patient/implant/therapy level factors associated with patient satisfaction and OHRQoL.

The data from the OHRQoL will be used to quantify overall satisfaction with implant therapy and quality of life post-implant therapy, and will be presented at each time point to explore any potential time trend. In addition to baseline demographics and clinical factors, the type and location of prosthesis as well as the different types of complications will be included in correlation analysis with the OHRQoL survey data (Table 2). Because the OHRQoL score is a continuous variable, mixed effects model will be used to examine the association between these patient/implant/therapy factors and the OHRQoL score to account for the longitudinal nature of the data.

Table 4.

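### OHRQoL and its change are a secondary objective in the synopsis and Section 3.2, but Section 11.3 analyses OHRQoL only as exploratory and states no contrast with baseline

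*Protocol*

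**What the plan says.** The protocol summary gives as a secondary objective "Assess patient OHRQoL (Oral Health-Related Quality of Life) and satisfaction with esthetics and function following implant therapy", and its outcome line reads "Secondary outcomes: Patient, surgical, prosthetic risk factors; biologic and prosthetic complications, and OHRQoL". Section 3.2 repeats the objective in its own row. There, "Patients will complete OHRQoL surveys at baseline and follow-up visits", the time frame places the first survey before insertion of the prosthesis, and the commitment is "Changes in the overall OHRQoL and patient satisfaction will be reported". Section 7.1 confirms that the baseline questionnaire asks about "oral health quality of life prior to prosthetic implant therapy".

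Section 3.3 makes a different OHRQoL question tertiary: "Explore factors predictive of patient OHRQoL (which includes satisfaction with esthetics and function").

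In Section 11.3 the Secondary Objectives cover only risk factors for biologic and prosthetic complications. OHRQoL first appears under "Tertiary (exploratory) Objectives. To explore the OHRQoL (Oral Health-Related Quality of Life) following implant therapy". The text there plans three things: presentation of the score at each time point to look for a trend, a correlation analysis with patient, prosthesis and complication factors, and a model: "Because the OHRQoL score is a continuous variable, mixed effects model will be used to examine the association between these patient/implant/therapy factors". Table 4 lists the factors. Age is the only item labelled as a baseline value, and the baseline OHRQoL score is not listed.

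**The concern.** There are two separate problems.

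First, a secondary objective loses both its tier and its measure between Section 3 and Section 11. A reader of Section 3.2 expects an estimate of how much OHRQoL changed after the prosthesis was placed. A reader of Section 11.3 finds a display of levels and an exploratory regression. The analyst would have to decide later whether a change is estimated at all, and at what tier it is reported.

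Second, the exploratory model compares groups such as single-tooth, splinted and full-arch removable restorations. These patients plausibly differ in OHRQoL before any study prosthesis exists. If the baseline score is not used, a factor's coefficient mixes that prior difference with whatever followed treatment. A poor score that preceded the prosthesis could then be read as a poor result of it.

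**Working it through.** **Passages side by side.**

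| Item | Summary and Section 3 | Section 11.3 |
|---|---|---|
| Assessment of OHRQoL | secondary (summary, 3.2) | tertiary |
| Measure | changes reported, survey before insertion and at years 1-3 (3.2) | score at each time point |
| Factors associated with OHRQoL | tertiary (summary, 3.3) | tertiary |
| Outcome of the factor model | OHRQoL score (3.3) | OHRQoL score |
| Baseline OHRQoL | collected (3.2, 6.3, 7.1, Appendix A) | not named in the text or Table 4 |

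Rows 1 and 2 conflict. Rows 3 and 4 agree. Row 5 is a silence.

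**Does the silence matter?** The protocol gives no SD, effect size or precision target for OHRQoL, so there is no figure to reproduce. The following inputs are assumptions, chosen only to show the mechanism:

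- 1400 patients (the largest N in Table 1 of Section 11.2), of whom 10% (140) have a given prosthesis type and 1260 do not;
- that group lies d = -0.5 SD from the rest at baseline;
- equal correlation rho between any two visits;
- the type has no effect once baseline is given.

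Section 11.3 allows two readings.

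*Follow-up scores only.* The coefficient is rho x d. Its standard error is sqrt(1/140 + 1/1260) x sqrt((1 + 2 rho)/3), and the first factor equals 0.0891.

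*Baseline as one of four responses, with a factor main effect and no factor-by-time term.* The coefficient is (d + 3 rho d)/4. Its standard error is 0.0891 x sqrt((1 + 3 rho)/4).

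| rho | Follow-up only (SD) | z | Baseline among responses (SD) | z |
|---|---|---|---|---|
| 0.3 | -0.15 | -2.3 | -0.24 | -3.9 |
| 0.5 | -0.25 | -3.4 | -0.31 | -4.4 |
| 0.7 | -0.35 | -4.4 | -0.39 | -4.9 |

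Under both readings the prior difference enters the coefficient. With the baseline score as a covariate the expected coefficient is 0. The variance of the year 1-3 mean falls from (1 + 2 rho)/3 to (1 + 2 rho)/3 - rho^2, which is 83%, 63% and 39% of its unadjusted value at rho = 0.3, 0.5 and 0.7.

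A simulation with 4000 patients and a smaller gap of 0.3 SD agreed with these formulas to within about 0.03 SD. Follow-up scores alone gave 0.11, 0.12 and 0.22 (expected 0.09, 0.15, 0.21). Baseline as a response gave 0.16, 0.17 and 0.24 (expected 0.14, 0.19, 0.23). The covariate form gave 0.02, -0.03 and 0.02.

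**Is the covariate the only remedy?** No. Suppose instead that the gap simply persists and both groups change equally. The covariate form then gives d - rho d = (1 - rho)d = -0.35, -0.25 and -0.15 SD, while a contrast of changes gives 0. Under the first assumption the contrast of changes gives (rho - 1)d = +0.35, +0.25 and +0.15 SD, while the covariate form gives 0. The two forms answer different questions, and the groups are not randomised, so the plan must say which one it asks.

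**The case against.** The strongest reply is that Section 11.3 does not exclude the baseline score. It says nothing of how baseline enters the model, its factor list is introduced as an addition to baseline clinical factors, and a statistical analysis plan could settle the matter. That stands: it would be wrong to say that the protocol decides to model OHRQoL without baseline. The tier conflict and the unmatched commitment to report change remain, because both lie inside this document.

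Second, a reader might infer that the whole OHRQoL analysis, including the Table 4 model, was demoted. The documents do not support this. The summary, Section 3.3 and Section 11.3 all make the factor model tertiary and describe it as an association with the score.

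Third, Section 3.2 speaks of changes and does not say change from baseline, and a display by time point could include the baseline visit. The wording point is fair. The survey before insertion, in the same row, makes change from baseline the natural reading, but a display of levels gives no estimate of change with its uncertainty.

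Fourth, a reader might take every complication to arise after baseline. Section 11.3 counts complications already present at baseline in its prevalence, so that is too strong.

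Fifth, the timing of the baseline survey is not entirely clear. Section 3.2 places it before insertion, whereas Section 4 has patient-reported data collected after office visits. The score may partly be recall of the earlier state. This limits what any baseline adjustment can achieve but does not remove the need for one.

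Last, the illustrative sizes follow from assumed inputs, and the zero after adjustment follows from assuming no effect given baseline. The calculation also leaves out the other model factors and clustering by practitioner. All of this stands.

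**Conclusion.** The point holds in two parts of different strength.

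The firm part is an internal contradiction: OHRQoL and its change are secondary in the summary and Section 3.2, while Section 11.3 provides only a tertiary treatment with no stated contrast to baseline. This needs no assumption beyond reading changes as changes from the survey before insertion.

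The weaker part is that the exploratory factor model, as described, leaves room for pre-treatment differences to enter its coefficients under either reading. The direction of the problem is clear if groups differ before treatment. Its size in this cohort is unknown. The 0.15 to 0.39 SD shown depends on an assumed 0.5 SD gap, a 10% group and correlations of 0.3 to 0.7. The documents do not support a claim that the study will report false therapy effects of that size, nor that covariate adjustment is the single correct analysis.

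**What to change.** In Section 11.3, list the OHRQoL analysis under Secondary Objectives, to agree with the summary and Section 3.2. Report the mean change from baseline at years 1, 2 and 3 with 95% confidence intervals from the mixed model.

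Keep the Table 4 model exploratory, and state how it accounts for the baseline score: either as a covariate for the year 1-3 scores, or as a time-0 response with factor-by-time terms. Say which is used and interpret the results as associations. Enter complications as status by visit, including those present at baseline.

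The cost is wording, since the baseline score is already collected. If the covariate form is chosen, patients without a baseline survey need that score imputed. The missing-data paragraph of Section 11.3 speaks only of imputing outcome values, so it would need a sentence to cover this.

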12 SOURCE DOCUMENTS AND ACCESS TO SOURCE DATA/DOCUMENTS

Each participating practice and the NCC will maintain appropriate research records for this study, using the principles of and complying with regulatory and institutional requirements for the protection of confidentiality of subjects. Each practice and the NCC will permit authorized representatives of NIDCR and regulatory agencies to examine (and when required by applicable law, to copy) research records for the purposes of quality assurance reviews, audits, and evaluation of the study safety, progress and data validity.

The following will be considered source documents for this study and will be maintained by the NCC via an EDC:

- Screening Log
- Baseline Patient Demographics Survey (completed by patient)
- Baseline Patient Characteristics Survey (completed by patient)
- Patient Contact Survey (completed by patient)
- Baseline Oral Health Quality of Life Survey (OHRQoL; completed by patient)
- Mucosal Characteristics Survey (completed by practitioner)
- Baseline Data Survey (completed by practitioner)
- Prosthetic Characteristics Survey (completed by practitioner)
- Radiographs of the study implants, collected at baseline and the 1-, 2-, and 3-year annual follow-up visits
- 1-, 2-, and 3-Year Patient Contact and Annual Follow-up Surveys
- 1-, 2-, and 3-Year Practitioner Annual Follow-up Surveys

All study source documents must be maintained in a secure manner, and authorized practice, ARC, or NCC personnel will have access to the source documents stated above.

13 QUALITY CONTROL AND QUALITY ASSURANCE

For quality management activities associated with data collection and processing, standard procedures for National Dental PBRN studies include automatic data quality checks in the EDC for each electronic CRF and the processes related to the manual review of data, discrepancy management, delinquent data handling, data updates, data verification and approval, and database audit. The EDC will be programmed with edit checks and response limiters to reduce data response errors. If out of range values are entered by the patient or provider, the individual will be alerted and asked to provide a value that is in range.

Reports will be created from the EDC system for the study team to address data accuracy and completeness. NCs will work directly with practices to address data discrepancies and/or missing data/CRFs. The PI will work closely with the NCC to ensure that the electronic CRFs are collected appropriately, and that confidentiality is being maintained according to protocol-specified procedures. Conference calls will be held approximately every month during the data collection phase with the study team and ARC and NCC personnel including NCs to monitor progress, manage study documentation and procedures, and troubleshoot any problems.

14 ETHICS/PROTECTION OF HUMAN SUBJECTS

14.1 Ethical Standard

The PI, study team, and ARC and NCC personnel will ensure that this study is conducted in full conformity with the principles set forth in The Belmont Report: Ethical Principles and Guidelines for the Protection of Human Subjects of Research, as drafted by the US National Commission for the Protection of Human Subjects of Biomedical and Behavioral Research (April 18, 1979) and codified in 45 CFR Part 46 and/or the ICH E6.

14.2 Institutional Review Board

The protocol and written information sheet will be submitted to the Central IRB for review and approval. Recruitment materials and all participant materials will undergo local context review by ceding IRBs. Approval of both the protocol and the consent form(s) must be obtained before any participant is enrolled. Any amendment to the protocol will require review and approval by the Central IRB before the changes are implemented in the study.

14.3 Informed Consent Process

Patients: Participating practices will designate who will execute consent procedures for the study. In most cases this will be the participating dentist. Any personnel who will be assigned to obtain consent will be defined as study personnel and must complete required IRB training. Consent procedures will be administered prior to performing any study-related assessments or procedures.

The patient's consenting process will be initiated via a conversation with the practitioner, pursuant to the overseeing IRB requirements. The practitioner or designee will explain the research study to the patient, answer any questions that may arise, and discuss risks and possible benefits of study participation, if applicable. If required by the responsible IRB, an electronic or paper consent form describing in detail the study procedures and risks will be given to the patient to read and review the document or have the document read to him or her. The participant will e-sign the consent document or give verbal approval of the consent process (depending upon central or regional IRB requirements), and a copy of the consent document will be emailed or given to the patient for his/her records if applicable. The consent process will be documented in the research record. Patients may withdraw consent at any time throughout the course of the study.

